Exclusion Criteria. Patients will only be excluded if they required immediate psychiatric intervention (i.e., self-inflicted injury, active psychosis), or are determined to be too psychiatrically distressed to be randomized to the control condition without acute psychiatric/mental health intervention, are not Washington, Oregon, Alaska, or California State residents, or are currently incarcerated; patients that do not speak English will also be excluded from the protocol. The trial will only include English speaking patients as prior study team investigation has previously documented over 40 different languages spoken by Harborview patients making the translation of consent documents and scales in multiple different languages impractical.^{103,104} Attempted consent for patients who are disoriented or delirious will be postponed; if a potential patient subject's combined score on the Glasgow Coma Scale (GCS)¹⁰⁵ is < 15 and/or questions 1 and 2 of Mini Mental Status Exam (MMSE)¹⁰⁶ is < 7 , the baseline interview will be postponed. Patients whose most recent COVID-19 test was positive will also be excluded.

Non-Entry (MD-3). As in the previous PCORI funded projects, in order to document reasons for study non-entry, whenever patients decline participation, the recruiter will inquire as to why they did not want to participate. Answers will then be recorded verbatim; in prior investigation, patient reasons for refusal fell into one of 5 categories that included inconvenience, privacy concerns, not interested in the study, undo distress, and refusal without giving a reason.

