Overview. The measures and timing of administration are described with references provided that document established scale psychometric properties (Table 1). All assessments have been previously employed by the study team in prior acute care medical investigations. The study also has prior experience translating interviews to Spanish. The plan for the translation of the scales in to Spanish will be as follows: as outlined in the Phase I processes, the study team will elicit from the study team stakeholders, comments and approval of final interviews and measures to be administered; this will occur in English. Once these interviews and measures are finalized and IRB approved, the study team will begin the translation process, which we anticipate will occur from September 1, 2018 through November 30, 2018. After the translated materials have been vetted and approved, recruitment of Spanish speaking patients would begin on or before January 1, 2019.

Table 1. Patient-reported Outcome Measures Delivered during Specified Interview Time Points

Scale	Complete Interviews					
	Baseline	1-month	3-month	6-month	9-month	12-month
Glasgow Coma Scale (GCS)	✓	–	–	–	–	–
Mini-Mental State Examination (MMSE)	✓	–	–	–	–	–
Injury Event	✓	✓	✓	✓	✓	✓
Posttraumatic Concerns	✓	✓	✓	✓	✓	✓
Demographic Characteristics	✓	–	–	–	–	–
PTSD Checklist (PCL) (DSM-IV)	✓	✓	✓	✓	✓	✓

PTSD Checklist (PCL) (DSM-5)	✓	✓	✓	✓	✓	✓
Patient Health Questionnaire Depression (PHQ-9)	✓	✓	✓	✓	✓	✓
Medical Outcomes Study 12-Item Short Form Health Survey (MOS SF-12)	✓	–	–	–	–	–
Medical Outcomes Study 36-Item Short Form Health Survey (MOS SF-36)	–	✓	✓	✓	✓	✓
Alcohol Use Disorder Identification Test (AUDIT-C 3-item)	✓	✓	✓	✓	✓	✓
Self-Report Health Service Utilization - pre-injury	✓	–	–	–	–	–
Self-Report Health Service Utilization - post-injury (since last interview)	–	✓	✓	✓	✓	✓
Medications	✓	✓	✓	✓	✓	✓
Single Item Drug and Tobacco	✓	✓	✓	✓	✓	✓
NSCOT Cognitive Screen (NSCOT)	✓	✓	✓	✓	✓	✓
Pain (Single item from SF-36) - pre-injury	✓	–	–	–	–	–
Pain (Single modified BPI item) - current	✓	–	–	–	–	–
Patient Satisfaction with Care	✓	✓	✓	✓	✓	✓
Employment/Work Status	✓	✓	✓	✓	✓	✓
Willingness for Treatment	✓	–	–	–	–	✓
Website and Smartphone Application Acceptability	✓	–	–	–	–	–
Reactions to Research Participation Questionnaire (RRPQ 1 item)	✓	✓	✓	✓	✓	✓
Trauma History Screen - pre-injury*	–	✓	–	–	–	–
Stressful Life Events	–	–	–	–	–	✓
CBT Items	–	–	–	✓	–	✓
Technology Use and Healthcare Utilization	–	✓	✓	✓	✓	✓

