Given challenges in recruiting a suitable injured Spanish-speaking peer, the team modified the plan for intervention delivery to use a translator to deliver the intervention to monolingual Spanish speakers (n=23, of which 11 were in the intervention arm and 12 were in the control arm). At the study COVID-19 recruitment pause in March of 2020, the team raised concerns about internal validity after noting significant differences in "peer dose" between the monolingual Spanish-speaking group of survivors and the rest of the study population (which included English speakers and bilingual Spanish speakers); peers were substantially less frequently involved in intervention activities for Spanish speaking patients when compared to English speaking patients. PCORI program staff and the DSMB agreed that further accrual of non-English speaking Spanish speaking patients should be discontinued. PCORI program also suggested a sub-analysis be conducted for the n=23 subgroup, including a dose response analysis and an analysis of Spanish speaking patients concern narratives. This academic product (e.g., manuscript, conference presentation) could highlight differences between the non-English speaking Spanish speaking group and the main study population. The academic product could also document specific challenges experienced by the monolingual Spanish-speaking group.

The overarching goal of this Spanish speaking sub-investigation was to assess the feasibility and acceptability of a culturally tailored intervention for monolingual Spanish-speaking injury survivors, delivered using a translator. The intervention was a sub-study contained within the larger comparative effectiveness trial. Non-English-speaking, Spanish-

speaking individuals were recruited and are being followed over the course of the year after their injury. At baseline in the trauma surgical ward, post-injury concerns were elicited and later transcribed and coded into concern domains. One-, 3-, 6-, 9-, and 12-month follow-up interviews reassess Spanish-speaking patients' post-injury concerns were reassessed. The follow-up assessments also reassess PTSD and depression symptoms, functional impairments, and health service utilization as patient reported outcomes. In addition, emergency department health service utilization is being followed for all patients, intervention and control, via the Emergency Department Information Exchange (EDIE) administrative platform.

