Harborview Medical Center collects, manages, and stores diagnostic, clinical care, and clinical outcome data for all patients admitted to Harborview with a trauma. This data is managed by the Trauma Registrar and maintained in accordance with RCW 70.168.060 and RCW 70.168.090. The Trauma Registrar is required by WA state law to protect information regarding specific patients and providers. Data elements involving identifying characteristics of individual patient's, providers', and the facility's care outcomes within the Trauma Registry must be kept confidential. The Trauma Registrar may release confidential information from the Trauma Registry in accordance with applicable laws and regulations (e.g., WAC 246-976-420). No other person may release confidential information from the Trauma Registry without express written permission from the registrar. Requests for Trauma Registry data reports are only approved on an official request form submitted by qualified agencies or individuals, consistent with applicable statutes and rules.

The study team will use the Trauma Registry to compare the demographic and injury characteristics of patients included in the trial with the characteristics of those patients who were admitted during the active recruitment period of the trial but were not included as study subjects. Additionally, some clinical variables of interest are only available in the Trauma Registry (e.g., injury severity). At the end of the trial, the study team will request a data pull from the Trauma Registry for all patients (consented and non-consented) admitted to Harborview during the active period of recruitment. The study team is requesting a waiver of consent and a HIPAA waiver in order to obtain Trauma Registry data for non-consented patients. This data may include ICD 10 codes and PHI such as admit date and demographic information that is associated with identifiers. The link between identifiers and de-identified data for consented and non-consented patient data from the Trauma Registry will be retained for the record retention period of six years after completion of the trial.

C. Data Sharing

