iv. Physical function. In prior comparative effectiveness trials conducted by the study team, at the 12-month time point, collaborative care patients demonstrated a mean MOS SF-36 PCS scale score of 43.7 (95% Confidence Interval = 41.0-46.5) and usual care patients demonstrated a mean MOS SF-36 score of 41.2 (95% Confidence Interval = 38.5-43.9).⁶⁷ Projecting these differences to the current investigation, with 20% 12-month attrition, 424 patients, the probability of a 2-tailed type I error set at 5%, correlation between observations of 0.7 and an anticipated effect size = 0.26, the power to detect differences in physical function will be ≥ 0.67 .

Aim 1. Additional COVID-19 Exploratory Analyses

The first step in the COVID-19 secondary analyses was to compare the baseline demographic and clinical characteristics of the pre- and post-COVID19 cohorts. The core aim of this analysis is to assess whether one impact of the pandemic has been to change the demographic, injury and clinical characteristics of study participants over time.

Next, informed in part by the RAPICE COVID-19 qualitative studies that the team had undertaken during the trial, it was decided to dichotomize the cohort into patients that did or did not have any follow-up assessment during the COVID-19 pandemic initiation in March 2020. In order to explore differential patterns of treatment response introduced by the COVID-19 pandemic, mixed effects regression models that included the 3-way interaction of treatment, by time, by COVID-19 cohort were performed. These regression models also incorporated comparisons of both intervention and control group effects, as well as isolated comparisons of pre- and post-COVID intervention group effects, at each time point.

IX. Additional Considerations Related to the Incorporation of Standards for Complex Interventions. (SCI-1 Fully

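### The exploratory pre-/post-COVID comparison of baseline characteristics may credit the pandemic with differences in ethnicity, language and possibly insurance that come from the trial's own closure of monolingual Spanish-speaking accrual

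*Combined protocol and SAP*

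**What the plan says.** All references are to the combined protocol and SAP.

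- **Section V, Exclusion Criteria:** "patients that do not speak English will also be excluded from the protocol". The same paragraph adds: "Patients whose most recent COVID-19 test was positive will also be excluded". Neither rule carries a date.
- **Section VI, Overview of outcome measures:** "recruitment of Spanish speaking patients would begin on or before January 1, 2019".
- **Section VI, COVID-19 modifications, part A:** a translator was used to deliver the intervention to "monolingual Spanish speakers (n=23, of which 11 were in the intervention arm and 12 were in the control arm"). The problem was raised "At the study COVID-19 recruitment pause in March of 2020", and the funder's staff and the DSMB agreed that "further accrual of non-English speaking Spanish speaking patients should be discontinued". The reason given is low peer involvement and its threat to internal validity.
- **Section VIII, Aim 1, Additional COVID-19 Exploratory Analyses:** the first step compares the baseline characteristics of the pre- and post-COVID cohorts. Its purpose is to "assess whether one impact of the pandemic has been to change the demographic, injury and clinical characteristics of study participants over time". The next step splits patients by whether any of their follow-up fell in the pandemic, and fits a treatment by time by cohort interaction.

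The Aim 1 text does not define the cohort boundary for the baseline step, does not say whether the 23 are included, and does not mention that the language rule changed.

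**The concern.** Two things changed at about the same time: the pandemic began, and the trial stopped taking monolingual Spanish speakers. The second was a decision about intervention delivery. It says nothing about who was being injured or who was willing to enrol.

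A comparison of participants across that date cannot separate the two unless both cohorts are put under the same language rule. As written, a drop in the Hispanic or Spanish-speaking share could be reported as an effect of the pandemic. Insurance could move with it, since the sub-study description lists lack of coverage among the themes to explore in this group. What is at stake is the reading of one descriptive table, not the treatment comparison.

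**Working it through.** **Inputs from the document.** Planned total 424 (Randomization). Monolingual Spanish speakers randomized: 11 + 12 = 23, which agrees with the stated 23 and is 23/424 = 5.4% of the planned sample.

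**Assumptions, because the document gives no figure.** The number enrolled before March 2020, N, is 200 to 300. All 23 are Hispanic. The Hispanic share among all other patients, h, is 8% to 20% and does not change over time. The 23 are within the 424 and are included in the comparison.

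**Split by enrolment date.** All 23 are before the boundary and none after.

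- Share before = (h(N − 23) + 23)/N. Share after = h.
- False fall = (23/N)(1 − h).

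The p-values are from an uncorrected chi-square test on the expected counts.

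| Before v after | h | Share before | Share after | False fall (points) | p |
|---|---|---|---|---|---|
| 200 v 224 | 8% | 18.6% | 8.0% | 10.6 | 0.001 |
| 200 v 224 | 20% | 29.2% | 20.0% | 9.2 | 0.03 |
| 250 v 174 | 12% | 20.1% | 12.0% | 8.1 | 0.03 |
| 300 v 124 | 8% | 15.0% | 8.0% | 7.0 | 0.05 |
| 300 v 124 | 20% | 26.1% | 20.0% | 6.1 | 0.18 |

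If 350 had enrolled before March 2020, p would be 0.16 to 0.34 over the same range of h.

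**Split by follow-up, as defined for the interaction models.** A patient injured after about mid-March 2019 has a 12-month interview due in the pandemic. Assume even Spanish-speaking accrual to 15 March 2020.

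- From 1 January 2019, 83% of the accrual window is exposed: 0.834 × 23 = 19 patients.
- From 1 December 2018, 78% is exposed: 0.779 × 23 = 18 patients.

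So k = 4 or 5 of the 23 are unexposed. With U unexposed patients (assumed 50 to 150):

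- Exposed minus unexposed share = (1 − h)[(23 − k)/(424 − U) − k/U].
- U = 50, k = 5, h = 8%: 0.92 × (18/374 − 5/50) = −4.8 points.
- U = 75, k = 4, h = 12%: 0.88 × (19/349 − 4/75) = +0.1 point.
- U = 150, k = 4, h = 8%: 0.92 × (19/274 − 4/150) = +3.9 points.

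Across these inputs p is 0.25 or higher.

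**Other characteristics, enrolment-date split.** If the 23 differ from the rest by d standard deviations on a continuous variable, the shift is (23/N)d. For d = 0.2 to 0.8 and N = 150 to 350 (wider than above), it runs from (23/350) × 0.2 = 0.01 SD to (23/150) × 0.8 = 0.12 SD.

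**Same language rule in both periods.** Dropping the 23 removes the language-closure shift by construction and leaves 424 − 23 = 401 patients.

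**The case against.** The strongest reply is that the artefact rests on things the plan does not state. The baseline step has no defined boundary, and the only split that is defined, by follow-up, gives almost no artefact. It is also unsettled whether the 23 are in these cohorts: the sub-study is described as sitting inside the larger trial, yet its patients are contrasted with the main study population and given their own sub-analysis. The analyses are labelled exploratory, the step does not compare arms, and the 23 are split 11 to 12.

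Most of this stands, and it is why the point is conditional and minor. It does not remove the point. The stated aim concerns change in participants over time, and the follow-up split is introduced only afterwards, so enrolment date is the natural reading of the first step. The separate sub-analysis of the 23 does not correct this comparison.

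Three stronger readings are tempting and should not be drawn:

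- **That the follow-up split makes the Hispanic share appear to rise.** Most of the 23 would probably be in the exposed cohort, but that cohort is also much larger. The difference in shares runs from about −5 to +4 points.
- **That the COVID-positive exclusion is a second artefact of the same kind.** That rule is itself an effect of the pandemic on who took part, and no count is given.
- **That injury type or the three-way model is materially biased.** The document gives no rates for injury type in this group, it does not say that the 23 enter the model, and no bias in that model has been quantified.

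**Conclusion.** The point holds in a limited form. If cohorts are split by enrolment date and the 23 are included, the language closure alone could produce a false fall in Hispanic share of about 6 to 11 points. Whether that reaches p < 0.05 depends on the unknown number enrolled before March 2020. Language is affected directly and insurance possibly; most clinical variables would shift little. The result rests on the assumed cohort sizes, the assumed Hispanic share among other patients, and all 23 being Hispanic. Severity is minor, and the intent-to-treat primary analyses do not change.

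**What to change.** In Aim 1, Additional COVID-19 Exploratory Analyses:

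1. Define the cohort boundary for the baseline step by enrolment date, and state whether the 23 are included.
2. Run the comparison restricted to patients eligible under the language rule of both periods, that is without the 23 (401 remain if they are within the 424). Show the all-patient version beside it.
3. Report how many patients were screened out for a positive COVID-19 test. The Patient Enrollment Log (section VII.B.2) already records reasons for exclusion.
4. Optionally, repeat the three-way interaction model without the 23 as a sensitivity check.

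It would also help to date the language rule, so that the Exclusion Criteria, the Spanish recruitment plan and the closure can be read together.

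The cost is a few lines of text and one rerun, with 23 fewer patients in one exploratory comparison. No new data are needed.

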c. PTSD Symptoms (PTSD Checklist).⁹² The PTSD Checklist, a 17-item self-report questionnaire, will be used to assess PTSD symptoms.⁹² The instrument yields both a continuous PTSD symptom score and a dichotomized diagnostic cut point for symptoms consistent with a DSM diagnosis of PTSD; the DSM-IV version will be used with 4 additional question criteria added so that either DSM-IV or DSM-V diagnostic criteria can be evaluated (see instrument appendix). A series of investigations have demonstrated the reliability and convergent and construct validity of the PTSD Checklist across trauma-exposed populations.¹⁷ Cronbach's alpha for the 17 item scale in a prior investigation with injured trauma survivors by the study team was 0.92.⁷¹ In a study of injured motor vehicle crash survivors, a correlation of 0.93 between the PTSD Checklist total score and the gold standard Clinician-Administered PTSD Scale diagnostic scale was documented.¹⁷

d. Physical Function and other Functioning and Quality of Life Outcomes (Medical Outcomes Study Short Form 36, MOS SF-36).^{117,119} The investigation will use the SF-36 to assess functioning and quality of life outcomes. Eight domains are assessed, including physical function, pain, general health, role physical function, role emotional function, vitality, social function, and mental health. The SF-36 has established reliability and validity and the measure has been used extensively with traumatically injured populations.^{96,117,118,120} The study team used the Physical Component Summary (PCS) sub-scale to assess post-injury physical function as a primary outcome. Cronbach's alpha for the MOS SF-36 PCS in prior investigations by the study team was 0.90.^{67,96}

Other patient reported outcome assessments. The investigation will use the PHQ-9 to assess depressive symptoms.^{114,121} The instrument yields both a continuous depressive symptom score and a dichotomized diagnostic cut point for symptoms consistent with a DSM-IV diagnosis of depression. The PHQ-9, item 9 asks specifically about suicidal ideation and/or intent. The PHQ-9 has established reliability and convergent and construct validity when used to assess patients

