VIII. Data Analyses. (IR-1 A priori Specific Plans for Data Analyses that Correspond to the Major Study Aims, IR-2 Assess Data Source Adequacy, IR-3 Describe Data Linkage Plans, if applicable, IR-5 Provide Sufficient Information in Reports to Allow for Assessments of the Study's Internal and External Validity, RQ-4 Identify and Assess [name]-1 Describe in Protocol Methods to Prevent and Monitor [name]-2 Use Validated Statistical Methods to Deal with Missing Data that Properly Account for Statistical Uncertainty Due to Missingness, MD-4 Examine Sensitivity of Inferences to Missing Data Methods and Assumptions, and Incorporate into Interpretation, HT-1 Examine Sensitivity of Inferences to Missing Data Methods and Assumptions, and Incorporate into Interpretation, HT-2 For all HTE Analyses, provide an analysis plan, including the use of appropriate statistical methods. HT-3 Report all Prespecified HTE Analyses and, at Minimum, the Number of Post-hoc HTE Analyses, Including All Subgroups and Outcomes Analyzed.)

Overview. All primary statistical analyses will be conducted with the intent-to-treat sample. The primary purpose of the statistical analyses is to examine and compare trends in emergency department health service utilization, posttraumatic concern severity, PTSD symptoms, and physical function longitudinally between patients in the peer-integrated collaborative care intervention and patients in the surgical team notification arms of the study. The major outcome variables are the continuous and dichotomous assessments of EDIE derived emergency department health service utilization,⁸³ patient reported posttraumatic concerns,^{69,86} PTSD symptoms (PTSD Checklist),⁹² and physical function (Medical Outcomes Study Short Form 36 (MOS SF-36).^{117,119}

The primary statistical analyses will test the hypothesis that patients randomized to the peer-integrated collaborative care intervention will demonstrate reductions in emergency department health service use when compared to patients randomized to the trauma surgery notification condition over the course of the 12-months after injury. Primary analyses will also assess whether collaborative care intervention patients demonstrate longitudinal reductions in posttraumatic concern severity and PTSD symptoms and improvements in physical function when compared to trauma surgery notification patients.

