The study team will use mixed effects regression models to test these hypotheses for both continuous and discrete outcomes.¹²⁸⁻¹³¹ The investigative group has extensive experience with this analytic approach in the analyses of longitudinal data after injury.^{20,24,47,67,68,71} In addition, these models will allow the use of covariates that model potential sources of non-response bias and time-dependent covariates. This type of model also allows the specification of random or fixed effects and the form of the serial correlation over time (if heterogeneity changes over time).

The effect of major interest will be the time by treatment group interaction term. For these models, repeated measurements of the baseline, 1-, 3-, 6-, 9-, and 12-month outcome assessments (i.e., EDIE documented emergency department utilization, concern severity, PTSD Checklist and MOS SF-36 Physical Components Summary (PCS) scale scores) will be the dependent variables. For all dependent variables, the study team will first fit models containing only time categories, intervention, and intervention by time interactions. The form of the dependent variables will determine the link function used.

The impact of including covariates in the model will be examined in planned sensitivity analyses (IR-5). As in prior study team investigation, sensitivity analyses will be used to assess the impact of key assumptions. Important injury and demographic characteristics, such as Injury Severity Score and age, will be entered into the models as covariates in planned sensitivity analyses. Prior to these analyses, the study team will examine baseline treatment group differences, using the appropriate statistics for the distribution of the variable. Although randomization should ensure balance between the two groups, it is essential to control for any known confounders in the design and analysis to prevent a biased assessment of the treatment effect. Any baseline injury, demographic, or clinical variables found to be statistically significant in this analysis will also be included as covariates in the regression models. Care processes will also be examined as part of the secondary data analytic plan.

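### The primary test is a time-by-treatment interaction with baseline as a response row, but for three of the four primary outcomes the plan does not supply that row as described

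*Combined protocol and SAP*

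**What the plan says.** The model is set out in section VIII, Data Analyses. "The effect of major interest will be the time by treatment group interaction term." The responses are "repeated measurements of the baseline, 1-, 3-, 6-, 9-, and 12-month outcome assessments", and the text lists ED use from the Emergency Department Information Exchange (EDIE), concern severity, the PTSD Checklist and the SF-36 Physical Component Summary (PCS). The first model contains categorical time, arm and their interaction, with the link chosen by the form of the outcome.

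The Overview of section VIII describes the aim in two ways. One is about trends: "The primary purpose of the statistical analyses is to examine and compare trends in emergency department health service utilization". The other, the lead hypothesis, is a reduction in ED use compared with "patients randomized to the trauma surgery notification condition over the course of the 12-months after injury".

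The baseline data are described elsewhere:

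- **Physical function.** Section VI.d: "The study team used the Physical Component Summary (PCS) sub-scale to assess post-injury physical function as a primary outcome." In Table 1 the row "Medical Outcomes Study 36-Item Short Form Health Survey (MOS SF-36)" has a dash at baseline and ticks from month 1 to month 12. The row "Medical Outcomes Study 12-Item Short Form Health Survey (MOS SF-12)" is ticked at baseline only.
- **Concerns.** The inclusion criteria (section V) require at least one severe concern, and section VI.b defines severe as a rating of 5. The power section uses only the yes/no form, any severe concern.
- **ED use.** Section VI.a describes EDIE as giving 12 months of follow-up. The only baseline utilization item in Table 1 is "Self-Report Health Service Utilization - pre-injury".

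The PTSD Checklist is collected in the same form at every visit and is not affected.

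**The concern.** What a time-by-treatment interaction tests depends on which rows enter the model. With a baseline row, where randomization makes the arms equal in expectation, a benefit at any later visit shows up as an interaction. Without that row, the term asks only whether the arm difference varies between months 1 and 12. A benefit that appears early and persists, which would be a good result, then contributes nothing.

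For three primary outcomes, including the lead one, the plan leaves open which of these tests will be run. An analyst who follows the text would find no SF-36 score at baseline, a concern variable with no variation at baseline, and no definition of baseline ED use. Each gap would have to be settled later, possibly after the data are seen, and the choice can change the conclusion.

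**Working it through.** **Inputs from the plan.** 424 patients, 1:1; two-sided 5%; correlation between observations 0.7; 20% attrition for patient-reported outcomes, so 424 × 0.8 / 2 = 169.6 per arm; no attrition for ED use, so 212 per arm; PCS effect size 0.26; ED rates 30/31/30% against 17/21/22% at 3-6, 6-9 and 12 months; any severe concern 74% against 52% at six months.

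**Assumed, because the plan does not give them.** The course of the effect over time for PCS and concerns, the ED rate at baseline, and the correlation structure (exchangeable unless stated).

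**1. The plan's PCS figure.** A single-time-point comparison gives z = 0.26 / √(2/169.6) = 2.394 and power Φ(2.394 − 1.96) = 0.668. This matches the stated 0.67.

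**2. Power of the interaction.** Let δ be the vector of arm differences by visit, S its covariance, and C the matrix of differences from the first row. Then λ = (Cδ)′(CSC′)⁻¹(Cδ), referred to a non-central chi-square with one degree of freedom fewer than the number of rows. For a single contrast with weights w, z = w′δ / √(w′Sw).

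**3. PCS.** Shapes are fractions of 0.26 at months 1, 3, 6, 9 and 12.

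| Shape | No baseline row (4 df) | With row, exchangeable 0.7 (5 df) | With row, autoregressive 0.7 (5 df) |
|---|---|---|---|
| Constant | λ = 0, power 0.05 | λ = 15.92, 0.89 | λ = 10.19, 0.69 |
| 1/3, 2/3, 1, 1, 1 | λ = 6.79, 0.53 | λ = 16.99, 0.91 | λ = 4.78, 0.35 |
| Linear to month 12 | λ = 10.46, 0.74 | λ = 14.71, 0.86 | λ = 3.72, 0.27 |

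The last column takes 0.7 as the correlation between successive visits. Under either structure a constant benefit without the row gives λ = 0.

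**4. ED use, with the plan's three windows.** The differences are 13, 10 and 8 points.

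- Interaction, follow-up rows only (2 df): λ = 2.44 on the risk scale, power 0.27; λ = 3.29 on the log-odds scale, power 0.35.
- Average difference: (13 + 10 + 8)/3 = 10.33 points; z = 2.76 on the risk scale and 2.75 on the log-odds scale; power 0.79 and 0.78.
- Interaction with an equal-arm baseline row, assumed rate 20 to 50% (3 df): power 0.90 to 0.98 over both scales.

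**5. Any severe concern.** At baseline the proportion is 1 in both arms, so its logit or probit is infinite and interactions with baseline cannot be estimated. A trial fit of the fixed-effects logit model with time categories, arm and interaction shows this: the standard error of the six-month interaction was 19 after 10 iterations, 2,839 after 20 and 34,590 after 25.

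If the baseline row is dropped, taking 74% in controls at every visit and 22 points as the full difference:

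| Course of the difference | Interaction | Average difference |
|---|---|---|
| Constant | 0.05 | above 0.99 |
| Month 1 at 80%, then full | 0.14-0.17 | above 0.99 |
| 1/2, 3/4, then full | 0.71-0.83 | 0.98-0.99 |
| 1/3, 2/3, then full | 0.94-0.98 | 0.97-0.98 |

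**The case against.** The strongest reply is that the plan does prescribe a baseline row, and every low power figure above comes from deleting it. The baseline data are not empty either. The SF-12 is collected at baseline, and the reference list entry for the 12-item form is cited in both section VI.d and the Overview of section VIII. Concern severity is rated 1 to 5 with no limit on the number of concerns, and the Overview allows continuous forms. A look-back EDIE extract may be possible. On this view the plan needs clarifying and has not been shown to be underpowered.

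Much of this stands. A reader might infer that no baseline row could be built for these outcomes. The documents do not show that. For PCS there is a conflict between the model and Table 1 that nothing bridges; a citation is not a scoring rule. For concerns the conflict applies to the only form that was powered. For ED use the row is undefined, which is not the same as unavailable.

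A reader might also infer that the power section was computed for a different test. That is not established. The plan names RMASS, a program cited for longitudinal designs with attrition, and states a correlation of 0.7, which a single-time-point comparison does not use. The PCS figure of 0.67 matches a single-time-point difference, and the interaction with a row under exchangeable correlation gives 0.86 to 0.91. The other figures are lower bounds of 0.80 and do not identify a test: for ED use the average difference gives 0.78 to 0.79, while the interaction with a row gives 0.90 to 0.98.

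The stated aim of comparing trends does fit an interaction, and visit-specific differences remain estimable because arm is in the model. None of them is named as the primary test, and the lead ED hypothesis is a reduction over 12 months, which a change-over-follow-up test does not address.

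**Conclusion.** The concern holds as a gap in specification that decides what the primary test is for three of the four primary outcomes. It is a direct conflict for PCS and for any severe concern, and an undefined row for ED use.

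If the row is missing, a constant benefit is detected with power 0.05, and the plan's own ED windows give 0.27 to 0.35. That does not show that power is low in every case: for PCS without a row it reaches 0.74 if the effect grows linearly.

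Nor does supplying a row guarantee high power. The PCS range of 0.86 to 0.91 rests on exchangeable correlation of 0.7, while section VIII leaves the form of the serial correlation open. Under the autoregressive structure the range is 0.27 to 0.69. The ED range of 0.90 to 0.98 also assumes exchangeable correlation, and a baseline rate that is equal in both arms.

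**What to change.** In section VIII, for PCS, concerns and ED use, name one treatment contrast per outcome as the primary test. Either form is acceptable:

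1. **A post-baseline arm difference, adjusted for baseline values already collected.** The covariates would be the SF-12 physical summary, the number or mean severity of concerns, and self-reported pre-injury service use. For PCS, a 12-month difference has power 0.668 unadjusted. Adjusted power is Φ(2.394/√(1 − r²) − 1.96), which is 0.71, 0.79 or 0.92 if the covariate correlates r = 0.3, 0.5 or 0.7 with the outcome (assumed values). For ED use, the average over follow-up matches the 12-month hypothesis, but its power depends on months 1 and 3, for which the plan gives no figures.
2. **A contrast against an explicitly defined baseline row.** The rows would be the SF-12 physical summary, a concern score that varies at baseline, and a pre-injury EDIE window.

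In both cases, do not use baseline any severe concern as a response row, state the primary concern score, and restate the power for the contrast named, with its assumed time course and correlation structure. The interaction can be kept as a secondary analysis. The PTSD Checklist model can stay.

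The cost is SAP wording and model code, with no new interviews. Under the first option, patients with baseline data only drop out of the concern and PCS models; the multiple imputation already planned can check the effect of this. Under the second, ED use needs a look-back EDIE extract, and the plan does not say whether one is available for every patient.
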